### **6 Minute Walk Test**

The objective of the test is to cover as much distance as possible within a six-minute time frame walking laps around 2 cones placed 100 ft apart in a straight path. The level of assistance and assistive devices used during the 6MWT and distance walked will be recorded.

### **Spinal Cord Injury Functional Ambulatory Index (SCI-FAI)**

The SCI-FAI is an observational gait assessment instrument that includes a 2-minute walk test of gait biomechanics and use of assistive device. This SCI ambulatory outcome measure is included as an observational assessment of the quality of the gait pattern. Physical therapists will score the SCI-FAI based on the first 2 minutes of the 6MWT. Video footage should be taken to assist with scoring.

### **Walking Index for Spinal Cord Injury II**

The Walking Index for Spinal Cord Injury II (WISCI II) measures the ability of an individual to complete a locomotor task in a standardized environment. The goal is to rank the severity of the underlying impairment in relation to function. The WISCI II has a total of 21 levels and includes information on the type of gait, bracing and assistive devices utilized and level of assistance walking while walking 10 meters or less. The WISCI II will be scored based on the 10MWT at self-selected speed using the current braces and devices as needed. Reliability of the WISCI II in SCI has been assessed in several publications including but not limited to: Marino et al., Burns et al. Completion time is less than 5 minutes.

### **Spinal Cord Independence Measure (SCIM-III, Mobility subscale)**

The SCIM was developed as a comprehensive rating scale specifically for persons with SCI. The instrument assesses independence in all aspects of primary daily activities relevant for patients with SCI; and scores every task or area of function according to its relative weight in the total relevant daily function. SCIM-III consists of 17 items in the following subscales: self-care, respiration and sphincter management, room and toilet mobility and mobility indoors, outdoors and on uneven surfaces. Scores range from 0-100. For the purposes of this study, only the mobility subscale of the SCIM-III will be completed via an interactive interview with the participant. Completion time is approximately 5-10 minutes. The mobility sub-scale consists of 9 items with a maximum score of 40.

### **Spinal Cord Injury Spasticity Evaluation (SCI-SET)**

The SCI-SET is a participant self-report composed of 35 items that assess the degree to which spasticity affects aspects of daily life activities over the past 7 days. Responses are on a 7-point scale that ranges from +3 (extremely helpful) to -3 (extremely problematic). The administration time is 3-9 minutes.

### **Center for Epidemiologic Studies Short Depression Scale (CES-D 10)**

The CES-D is a screening tool measure developed to identify current depressive symptomatology related to major or clinical depression in adults and adolescents. Items include depressed mood, feelings of guilt, worthlessness and helplessness, psychomotor retardation, loss of appetite, and sleep difficulties. There are 10 and 20 item versions of the scale. The most commonly used version of the CES-D is the 10 item version (CES-D 10) which was developed in the 1970's by Lenore Radloff (researcher at National Institute of Mental Health).

### **Borg Rating of Perceived Exertion**

The Borg Rating of Perceived Exertion (RPE) is a way of measuring physical activity intensity level. Perceived exertion is based on the physical sensations a person experiences during physical activity, including increased heart rate, increased respiration or breathing rate, increased sweating, and muscle fatigue. Participants are asked to rate their maximal perception of exertion of physical activity during a session and during the 6MWT. The severity is measured either on the original scale of 6-20 (6 meaning no exertion at all and 20 meaning maximal exertion).

### **Numeric Rating Scale (NRS) for spasticity and pain**

The Numeric Rating Scale is a participantself-report on a 0-10 scale of overall spasticity or overall pain over the past week. Zero denotes no spasticity/pain, and 10 denotes "worst spasticity/pain imaginable." Completion time for both, inclusive, should be no more than 5 minutes.

### **NASA Task Load Index for self-reported work load**

The NASA Task Load Index is a 6-item, subjective, multidimensional assessment tool that rates perceived workload during a task, or other aspects of performance. The questions include rating physical and mental workloads, as well as psychological/emotional reactions to the workloads. It was developed by NASA Ames Research Center's (ARC) Sandra Hart in the 1980s and has become the gold standard for measuring subjective workload when working with human-machine interface systems. Completion time is no more than 5 minutes.

# 1 STATISTICAL ANALYSIS PLAN

## 1.1 Data Analysis Methods

The following guidance documents and standards have been consulted for the development of this study design and statistical analysis plan:

- Title 21 – Food and Drugs Chapter 1 – Food and Drug Administration Department of Health and Human Services, Subchapter H – Medical Devices, Part 890 – Physical Medicine Devices, Subpart D – Physical Medicine Prosthetic Devices, Sec. 890.3480 Powered Lower Extremity exoskeleton.
- Guidance for Industry and/or FDA Reviewers/Staff – Guidance Document for the Preparation of IDEs for Spinal Systems, January 13, 2000.
- Guidance for Industry and FDA Staff – Spinal System 510(k)s, May 3, 2004.
- Investigational Device Exemptions (IDEs) for Early Feasibility Medical Device Clinical Studies, Including Certain First in Human (FIH) Studies: Guidance for Industry and Food and Drug Administration Staff, October 1, 2013.
- Design Considerations for Pivotal Clinical Investigations for Medical Devices: Guidance for Industry, Clinical Investigators, Institutional Review Boards and Food and Drug Administration Staff, November 7, 2013.
- Guidance for Industry, E9 Statistical Principles for Clinical Trials, FDA, 1998.
- Guidance for Industry, Patient-Reported Outcome Measures: Use in Medical Product Development to Support Labeling Claims, FDA, December 2009
- Statistical Guidance for Clinical Trials of Non-Diagnostic Medical Devices, FDA, 1996.
- Clinical Investigation of Medical Devices for Human Subjects –Good Clinical Practice ISO 14155:2011).

This study design involves outcome variables measured on binomial, ordinal, and continuous scales. For the continuously scaled outcome variables (i.e., 10MWT, 6MWT, WISC-II Score, etc.), the general situation applies analysis of variance and covariance when there are  $g$  distinct groups with a sample of observations for each group. The general null hypothesis is that the outcome variable distribution is the same for the treatment and the active control group. The assumptions associated with the analysis of variance are: 1) the  $g$  samples are independent random samples, 2) the observations in group  $i$  (for each  $i = 1, 2, \dots, g$ ) are a random sample from a normal probability distribution with mean  $\mu_i$  and variance  $\sigma_i^2$ , and 3) the  $g$  population variances,  $\sigma_1^2, \dots, \sigma_g^2$ , are equal to a common variance  $\sigma^2$ . Inherent to these assumptions is the assumption of a linear additive model with equal sample sizes. There are a variety of statistical procedures for the comparison of means in an analysis of variance setting. In the case of unequal sample sizes and multiple endpoints, the Scheffe's or Bonferroni procedures are appropriate to control for experiment-wise multi-comparison error (Woolson, 1983). If the assumption of normal distributions is not met, rank analysis of variance is used. More common rank analysis of variance tests are Kruskal-Wallis and Friedman tests. In addition, paired t-Test will be used for paired data since this is a single group matched-pairs design with the assumption that the pairwise differences are normally distributed.

Multiple comparison analysis (repeated measures) of ordinal or nominal-scale data (i.e., 5-point Likert type scales, numeric rating scales, etc.) generally assumes a logit model. This type of model uses cumulative logits, which automatically take the ordinality of the data into account. If the assumptions associated with this model are met, tests of uniform association and proportional odds can be computed. If, however, maximum likelihood estimation is desirable, generalized logits are computed from a log-linear model (Agresti, 1990 and Stokes et al., 1995).

The standard formulation for the analysis of binomial variables (i.e., Occurrence of an Adverse Event, Yes or No, etc.) typically entails testing a null hypothesis of no association between the treatment groups and outcomes. Chi-square and likelihood ratio statistics, for which the appropriateness depends on the linearity of the data, are computed for this analysis. In addition, two-sample chi-square tests of equivalence will be computed. Moreover, since single-group pre- and post-test comparisons are anticipated, McNemar's test for matched pairs is appropriate since the assumption of independent samples cannot be met (McNemar, 1947). Agresti (1990, pp. 348) has also proposed several alternative methods for comparing dependent proportions. Exact probabilities will be reported when appropriate.

The study design includes a run-in period where the first 1 to 4 participants at each site will be assigned. Those participants who meet study entrance criteria during that run-in period will be randomized on a 2:2:1 ratio to one of three treatment groups; the Ekso G Intervention Group, the Active Control Group, or the Passive Control group. The participants who are assigned to the Ekso intervention will receive GT robotic gait training 3 times per week for 12 weeks (36 sessions). The goal is a minimum of 300 steps of gait training in the Ekso GT per 45 minute session. Overground walking starts when Participants require only minimal assistance of one therapist and one aide to assist with assistive device, without any BWS, for at least 10 meters. This will be assessed every 3rd session during the 10MWT. At this point, sessions will consist of 30 minutes of gait training in the Ekso, followed by 15 minutes of standard overground gait training without BWS for a total of 45 minutes of walking.

Intent-to-treat population:	Subjects who met the inclusion criteria and were randomized to an intervention arm. Thus, enrolled in the study.
All enrolled population:	Subjects who were enrolled in the study (randomized to an intervention arm) and completed at least one day of the intervention. This group of subjects will be used for safety analysis.
Per protocol population:	All subjects who were enrolled, completed one of the three intervention arms, and were followed out to last follow-up visit after following intervention.

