- 21. Uncontrolled or severe orthostatic hypotension that limits standing tolerance; defined as sustained, symptomatic drops in systolic and diastolic blood pressure when moving from sitting to standing
- 22. Active heterotrophic ossification (HO), hip dysplasia or hip/knee axis abnormalities
- 23. Colostomy
- 24. History of long bone fractures since the SCI, secondary to osteoporosis
- 25. Unable to sustain current medication regimen, specifically those medications that may impact study outcomes (such as spasticity).
- 26. Any reason the physician may deem as harmful to the participant to enroll or continue in the study

Treatment Groups: **Run-In Group:** The first 1 to 4 Participants at each site will be assigned to the Run-in Group. The Run-in Group follows the Group 1 assignment described below. After the site has completed the Run-in phase, Participants who meet study entrance criteria will be randomized to one of three groups:

**Group 1:** Ekso Intervention - Participants in this group receive Ekso GT robotic gait training 3 times per week for 12 weeks (36 sessions). The goal is a minimum of 300 steps of gait training in the Ekso GT per 45 minute session. Overground walking starts when Participants require only minimal assistance of one therapist and one aide to assist with assistive device, without any BWS, for at least 10 meters. This will be assessed every 3rd session during the 10MWT. At this point, sessions will consist of 30 minutes of gait training in the Ekso, followed by 15 minutes of standard overground gait training without BWS for a total of 45 minutes of walking. See Table I A for the training progression strategy and section 10 – Training Regimen and Rules for details.

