## 5. Participant Enrollment

Participants will be identified and recruited from outpatient clinics. Participants will be presented with a study consent form. The point of enrollment is after the patient has met the inclusion/exclusion criteria, and has signed the study consent form. Run-in Participants (the first 1 to 4 recruited) are to be consented using the Run-in consent form. Run-in Participants follow the same assignment as described in Group 1 but are NOT randomized. After the Run-in phase, subsequent Participants are consented using the Randomized Consent Form and then randomized to Group 1, Group 2, or Group 3. This is further detailed in the section on "Screening and Informed Consent."

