**Applicants become enrolled as Participants in the study upon signing the consent form.** The original signed consent form will be returned to the investigator and filed in the Participant's study file; the Participant will be given a copy of the signed consent to keep.

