An independent Data Safety Monitoring Board (DSMB) will assess and adjudicate all SAEs and protocol violations.

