## **17. Statistical Methods**

### **17.1 General Principles**

The primary analysis for all baseline characteristics and study outcomes will include all available data for all enrolled subjects. Standard summary statistics will be calculated for all study variables. For continuous variables, statistics will include means, standard deviations, medians and ranges. Categorical variables will be summarized in frequency distributions.

Statistical analyses will be conducted according to the principles of intent-to-treat, under which subjects will be evaluated according to their randomized assignment regardless of the treatment actually received. P-values for tests of superiority will be two-sided and for non-inferiority one-sided, with values less than 0.05 deemed statistically significant.

Statistical analyses will be conducted in SAS version 9.3 or above (SAS Institute, Cary, N.C.), R version 3.2 or above (R Foundation for Statistical Computing, Vienna, Austria, <http://www.R-project.org>) or another validated statistical software package.

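### The SAP's intent-to-treat definition carries an eligibility condition that, read literally, drops randomised participants later found ineligible; no SAP population is simply all randomised

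*SAP*

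**What the plan says.** SAP section 1.1 lists three analysis populations and applies its analyses to each.

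- **Intent-to-treat:** "Subjects who met the inclusion criteria and were randomized to an intervention arm", followed by the gloss "Thus, enrolled in the study".
- **All enrolled:** randomised and completed at least one day of the intervention; used for safety.
- **Per protocol:** enrolled, completed one of the three arms, and followed to the last visit.

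Protocol section 17.1 says that the primary analysis "will include all available data for all enrolled subjects", and that under intent-to-treat "subjects will be evaluated according to their randomized assignment regardless of the treatment actually received". It attaches no eligibility condition.

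The protocol places enrolment at two different points. Section 5 says: "The point of enrollment is after the patient has met the inclusion/exclusion criteria, and has signed the study consent form". Section 8.1 says: "Applicants become enrolled as Participants in the study upon signing the consent form".

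The intended sequence is in the Study Outline: "Participants who meet study entrance criteria will be randomized to one of three groups". Section 26 has monitors check that only eligible people are enrolled, and has variances recorded and reported.

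**The concern.** The SAP definition joins two conditions, and a programmer building the analysis set would have to apply both. A participant randomised in error on, say, strength, range of motion or walking speed would then be dropped from the set meant to preserve the randomised comparison. The SAP does not say who judges eligibility, when, from which data, or whether that person is blind to arm.

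Therapists and participants know which training is given. If eligibility were re-examined after allocation, removals could differ between arms. Both primary comparisons, superiority to passive control and non-inferiority to active control, would be exposed. Removing poor performers from the Ekso arm alone would favour Ekso in both.

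**Working it through.** **1. Do the populations include one that is all randomised?**

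| Set | Condition beyond randomisation |
|---|---|
| SAP intent-to-treat | Met the inclusion criteria |
| SAP all enrolled | At least one day of intervention |
| SAP per protocol | Completed the arm and followed to the last visit |
| Protocol 17.1 | None stated, but rests on the word enrolled |

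None of the three SAP sets is all randomised. Take a participant who is randomised, found to miss an inclusion criterion, and never trained. Read literally, that person is in no SAP population, while Protocol 17.1 states no ground for leaving the person out.

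**2. Inputs for size** (Protocol 17.2 and 17.4; SAP 1.3 and 1.8). Ekso: mean change 0.11 m/s, SD 0.18. Active control: 0.078, SD 0.108. Passive control: 0, SD 0.108. Margin 0.055. Evaluable numbers 38, 38 and 19. Alpha is 0.05, two-sided for superiority and one-sided for non-inferiority.

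**3. The plan's own sample size reproduces.**

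- Superiority, 38 against 19: SE = √(0.18²/38 + 0.108²/19) = 0.0383. Then 0.11/0.0383 = 2.87, and power = Φ(2.87 − 1.96) = 81.9% (80.5% by the Welch t version).
- Non-inferiority, 37 per group: SE = √((0.18² + 0.108²)/37) = 0.0345. Then (0.055 + 0.032)/0.0345 = 2.52, and power = Φ(2.52 − 1.645) = 81.0% (80.2% by Welch).

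These figures are not in dispute.

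**4. Shift in the mean.** If k of n participants, each one SD below their arm mean, are removed, the arm mean rises by k × SD/(n − k). All values of k are assumptions.

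- One Ekso removal: 0.18/37 = 0.0049 m/s, or 9% of 0.055.
- Three Ekso removals, none from control: 3 × 0.18/35 = 0.0154 m/s, or 28% of 0.055.
- Balanced case. Five of 95 removed in proportion to 2:2:1 is two Ekso, two active and one passive. If all are at −1 SD, Ekso rises by 2 × 0.18/36 = 0.010 and active by 2 × 0.108/36 = 0.006. The net shift between them is 0.004 m/s, or 7% of the margin.
- Removals unrelated to outcome: expected shift zero.

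A different assumption is that a fraction f is removed from Ekso only, with zero mean change among those removed. The shift is then 0.11/(1 − f) − 0.11. For f = 2%, 5% and 10% this is 0.002, 0.006 and 0.012 m/s (4%, 11% and 22% of the margin).

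**5. Power** (Welch; the same assumed fraction removed from every arm, rounded to whole participants).

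| Removed | Ekso / active / passive | Superiority | Non-inferiority |
|---|---|---|---|
| 0% | 38 / 38 / 19 | 80.5% | 81.1% |
| 2% | 37 / 37 / 19 | 79.9% | 80.2% |
| 5% | 36 / 36 / 18 | 78.3% | 79.2% |
| 10% | 34 / 34 / 17 | 75.8% | 77.1% |

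The allowance from 95 to 127 could absorb this loss of power. It cannot remove a bias.

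**The case against.** The strongest reply is that the SAP phrase describes and does not exclude. The gloss "Thus, enrolled in the study" and the next definition, which equates enrolled with randomised, suggest that the author had the ordinary sequence in mind. The Study Outline and the design description in SAP 1.1 both put eligibility before randomisation. This stands as a possible reading. It does not settle the matter, because the sentence is the operative definition of an analysis set and its literal terms are conditions.

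Four stronger inferences are tempting and are not supported.

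- **That the SAP flatly contradicts the protocol's intent-to-treat sentence.** The closing words of "subjects will be evaluated according to their randomized assignment regardless of the treatment actually received" concern treatment received, not eligibility. The tension is with the reference to all enrolled subjects and with analysis by assignment. Under section 5, enrolment itself presupposes eligibility; under section 8.1 it does not. The protocol is therefore not a clean unconditional rule.
- **That the data safety monitoring board could remove people once outcomes are known.** Protocol section 12 says that it "will assess and adjudicate all SAEs and protocol violations". That gives it no authority over analysis sets, and section 26 speaks of recording and reporting variances, not of removal. No removal step is written anywhere.
- **That the Ekso-specific device criteria in Protocol section 9 create one-sided removal.** Those criteria come from the operating manual and are not the SAP's inclusion criteria. Fitting the device is already required of every entrant.
- **That loosely worded criteria make later exclusion easy.** Terms such as approximately and near normal may equally make it harder to declare someone ineligible in retrospect.

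Two further points temper the concern. Outcomes are collected by blinded evaluators, although this protects measurement and not membership of the set. The all-enrolled population has no stated eligibility condition, so comparing results across populations might reveal a marked effect of removal.

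**Conclusion.** The point holds as a defect in the definition. Applied literally, the SAP's intent-to-treat set loses any randomised participant later found to miss an inclusion criterion, and no other SAP set restores all randomised participants. The condition names inclusion criteria only, so breach of an exclusion criterion is not covered. The documents do not show that such exclusions are planned.

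The effect cannot be sized from the documents, because they give no rate of ineligible randomised participants. It could be nil. A reader might take 28% of the margin as the likely bias. That figure needs three removals, all from Ekso, all at −1 SD, with none from active control, and should be read only as an assumed worst case. The change is still worth making: the present wording permits exclusion after randomisation in both primary comparisons and brings no benefit in return.

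**What to change.** In SAP 1.1, define the intent-to-treat population as all randomised participants in all three groups, analysed in the group to which they were assigned, with no eligibility condition. Align Protocol 17.1 by replacing its reference to enrolled subjects with randomised participants, since sections 5 and 8.1 define enrolment differently.

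If an analysis without ineligible participants is wanted, place it in the per-protocol set or a named sensitivity set. State that eligibility is judged from data recorded before randomisation, by someone blind to arm and outcome.

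The cost is one sentence in SAP 1.1, the rule for the secondary set, and a one-word alignment in the protocol. No additional data or participants are needed. If the eligibility phrase was only ever descriptive, removing it changes nothing.
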